### **3.8.3 Image analysis with SPM:**

*Rationale for using SPM.* The traditional method for analyzing brain SPECT images involves the placement of a number of ROI's on the image (as described above), and measuring the mean counts within that ROI. It has long been known that ROI definition, particularly on functional images, is time-consuming, subjective and prone to operator bias (64). Small regular ROI's are capable of resolving localized changes between images, although they are subject to a loss of specificity due to problems associated with multiple comparisons. Alternatively, large ROI's encompassing an entire brain structure may dilute small activation foci with a subsequent loss of sensitivity. Unless a study is strongly hypothesis driven, and comparisons between images are *only* made in highly specific regions; ROI analysis lacks the power to distinguish regional variations between a set of images accurately. The solution to this problem has been the development of pixel-based statistical analyses where the regions are effectively reduced to single pixels (65). Our group has applied SPM, and other voxel-based techniques, to cerebral blood flow and binding site studies previously (66) and has considerable experience in these methods.

*SPM analysis.* A typical SPM analysis of a set of brain scans can be reduced to three essentially independent steps: image normalization, statistical analysis, and significance assessment. Once images are normalized to a standard template, pixel-by-pixel statistical tests are performed comparing the individual scans and correcting for inter-scan and inter-subject variability. This leads to the generation of (uncorrected) parametric images of significant differences. In the absence of absolute quantification, an important feature of SPM is the method of normalizing each individual scan to prevent inter-subject and inter-scan variability masking regional changes. The regional activity is normalized to a reference value derived independently from each image. This reference must accurately reflect an unbiased baseline of activity not affected by the disease or activation under study. For cerebral binding sites, the normalizing factor is usually a measure of background activity such as counts in the cerebellum. This is the background region used in the equilibrium model of DaTSCAN binding, giving a semi-quantitative measure of tracer uptake that is proportional to the binding potential.

*Significance assessment.* The statistical parametric maps represent significant differences at the pixel-level. However, in a typical brain image, there are many thousands of pixels, and the probability that many of them will be significant purely by chance is high, even for tight thresholds. The final step in SPM assesses the significance of *clusters* of suprathreshold pixels, correcting for the effects of such a large number of correlated multiple comparisons using the theory of random Gaussian fields. Statistically significant differences between and baseline and post-treatment scans will be assessed at each voxel with a threshold of  $P < 0.001$ . To correct for correlated multiple comparisons, clusters of voxels which survive this threshold will be assessed further using the theory of random Gaussian fields (67,68), which calculates the significance of clusters based on their peak height and spatial extent. Due to the limited volume of the striatum, the small volume correction will be used within SPM, allowing a more sensitive test. With this technique, differences in DaTSCAN binding between baseline and post-treatment scans will be assessed, and statistic images generated showing significant regional differences. A correlational analysis with various neuropsychological parameters such as the UPDRS, profile of mood scale, and Parkinson's Disease Questionnaire will also be performed with SPM. Similar analysis will be performed for the MRS data, which will compare the concentration of the specific molecules measured by MRS before and after three months of the nutritional supplementation program.

**3.8.4 Power Analysis:** We view this study primarily as a pilot study to assess changes in physiological and clinical measures and determine the effect size for powering future, larger trials. However, we estimated the sample size needed based upon prior research we have performed evaluating DAT imaging in the study of PD patients. We have previously found that the PD patients can have variability in their DVR measures of dopamine binding of approximately 10%. If we expect a 5-10% improvement in the treatment groups, for an 80% power to detect a significant change of  $p=0.05$ , we would need approximately 28 subjects in the treatment arms and approximately 14 subjects in the control arm. The statistical analyses for the proposed study will consist of 1) repeated measures two-way ANOVA, and 2) linear regression. Both methods are more powerful than simple t-tests on which these estimates are based. Thus, we plan to recruit up to 65 subjects, to allow for attrition which could be as high as one third, who would then be randomized into the two groups in a 2:1 ratio until the groups are complete.

3.8.5 Randomization: Randomization will occur via a 2:1 ratio of the NAC group and the waitlist control groups using the method of random permuted blocks with random block sizes without stratification.

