To receive a diagnosis of clinically probable Parkinson's disease, the disease must be progressive, and at least two of the three cardinal signs of PD must be present (bradykinesia, rigidity, and tremor). Additionally, at least two of the following must also exist: (a) asymmetry of signs, (b) asymmetry at onset, (c) absence of characteristics of alternative diagnoses, (d) absence of another etiology known to cause similar features (e.g. neuroleptics).

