## 3.8 Statistical Considerations

**3.8.1 Descriptive and Exploratory Analyses:** The initial analyses of the data will be descriptive in nature. Using means, standard deviations, median, and range, the distribution volume ratios (DVRs) will be described for each time point before and after subjects have used the nutritional supplementation for approximately 90 days. Similarly, the clinical scores will be described for each time point. Graphical methods, such as plots of measurements over time, histograms, and boxplots are important tools for understanding the quality of the data, and assessing assumptions underlying statistical models (such as normality). Transformations will be applied as necessary to satisfy these assumptions. Plots of all of the measured variables over time will be important to assess longitudinal patterns of change.

**3.8.2 Analyses for Primary Objectives:** To evaluate whether intravenous/oral NAC helps to support dopamine function in the brain of patients with PD by measuring changes in the dopamine transporter. To accommodate the longitudinal nature of the data, a Heterogeneous Random Coefficients Model (62,63) will be fit for the DVRs in each region for the DaTSCAN binding and each neurobehavioral score (i.e. UPDRS scores). This model can also account for both between and within subject heterogeneity and will accommodate modeling potentially nonlinear therapeutic effects over time. The random coefficients model is more flexible in terms of modeling the changes in DVRs and neuropsychological tests over time than repeated measures analyses of variance. The random coefficients model also has fewer restrictions on the correlation structure between multiple measures within subjects. ANCOVA will be used in order to determine if there are correlations between the pre-intervention neuropsychological and clinical measures and the longitudinal outcome measures after receiving oral or intravenous supplementation. This analysis will also evaluate whether the DaTSCAN DVRs can be utilized as a predictor for outcome. To determine if there is a correlation between changes in DAT binding and symptom severity, Pearson product-moment correlations will be computed unless the normality assumption is violated, in which case the Spearman rank correlation will be computed.

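### Nothing in the imaging analysis aligns subjects by disease side, so a DAT change that differs between the more and the less affected striatum would be diluted

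*Combined protocol and SAP*

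**What the plan says.** Section 3.8.3 gives the SPM sequence as normalization, testing and significance assessment: "Once images are normalized to a standard template, pixel-by-pixel statistical tests are performed comparing the individual scans". Its significance paragraph adds: "Statistically significant differences between and baseline and post-treatment scans will be assessed at each voxel with a threshold of" P < 0.001, followed by cluster inference with a small volume correction.

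For the regional analysis, section 3.8.2 states that a random coefficients model "will be fit for the DVRs in each region for the DaTSCAN binding". The regions are not listed. Section 3.7.1 places standardized template ROIs and makes their specific uptake values the primary outcome measure. It does not say whether left and right are kept apart, averaged, or relabelled by disease side.

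Section 3.1 includes among its four supporting diagnostic features "a) asymmetry of signs, (b) asymmetry at onset", and requires at least two of the four. Nowhere does the document record the more affected side for the imaging analysis, mirror scans by it, or adjust for it.

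**The concern.** The document recognizes that signs and onset can be asymmetric, yet its image analysis has no place for side. If scans go unmirrored to a common template, a left putamen voxel holds the more affected striatum of some subjects and the less affected striatum of others. A treatment-related change that is larger on one disease side would then lie on the left in some subjects and on the right in others. The average at any one location shrinks and its variance grows.

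Objective 2.1.2 depends on these images. Section 3.8.3 argues for SPM on the ground that large regions can dilute small focal changes; mixing disease sides would bring dilution back, across subjects. Section 3.8.4 also says the pilot is meant to supply an effect size for later trials, and a diluted estimate would carry over into that planning. Undefined laterality also leaves the choice of region open until the data have been seen.

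**Working it through.** **The plan's own figure (section 3.8.4).** The inputs are "variability in their DVR measures of dopamine binding of approximately 10" per cent, "If we expect a 5-10% improvement in the treatment groups", and "for an 80% power to detect a significant change of" p=0.05, giving "we would need approximately 28 subjects in the treatment arms and approximately 14 subjects in the control arm". The estimates rest on simple t-tests. I assume a two-sided test and 2:1 allocation.

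- Normal formula, controls: (1 + 1/2) × (1.960 + 0.842)² × 10² / 10² = 11.8, so 12 controls and 24 treated. The exact t-test gives 13 and 26.
- With 28 and 14, power at a 10-point difference is 85%, and 80% power is reached at 9.4 points.
- At 5 points the need is 48 and 96, and power with 28 and 14 is 32%.

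The stated size therefore reproduces only near the top of the 5-10% range, so I use 10 points below.

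**Assumptions not in the documents.** The 10% is the SD of one side's change, in a region and at a voxel. The more affected side is left in half of the subjects. The left-right correlation of the change, ρ, runs from 0 to 0.8. The controls show no change.

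**SPM, before versus after, n = 28, two-sided 0.001 (critical t = 3.69 on 27 df).** Let the change be a on the more affected side and b on the less affected side, with a share p of subjects more affected on the side examined. At a fixed voxel:

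- mean = p·a + (1 − p)·b
- SD = √(10² + p(1 − p)(a − b)²)
- noncentrality = √28 × mean / SD

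Results:

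- Aligned, a = 10: √28 × 10/10 = 5.29, power 93%.
- Fixed, 10 and 0, p = 0.5: mean 5, SD √125 = 11.18, noncentrality 2.37, power 12%.
- Fixed, 10 and 0, p = 0.7: mean 7, SD √121 = 11.0, noncentrality 3.37, power 40% on the commoner side.
- Fixed, 10 and 5, p = 0.5: mean 7.5, SD √106.25 = 10.31, noncentrality 3.85, power 57%.
- Equal changes of 10: mean 10, SD 10, power 93%, aligned or not.

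SPM searches both striata. By simulation, detection on at least one side with p = 0.5 is 21-24% for 10 and 0, and 71-83% for 10 and 5, across the range of ρ.

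**Regional contrast, 28 versus 14, two-sided 0.05.** The standard error factor is √(1/28 + 1/14) = 0.327. Aligned, the noncentrality is 10/(10 × 0.327) = 3.06, power 85%. Mixing raises the SD in the NAC arm only, so the fixed-side figures are simulated. For a bilateral mean the SD is 10√((1 + ρ)/2), from 7.07 to 9.49.

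| Change, more / less affected side | Fixed left or right region | Bilateral mean | More affected region |
|---|---|---|---|
| 10 / 0 | 27% | 35-56% | 85% |
| 10 / 5 | 59% | 65-89% | 85% |
| 10 / 10 | 85% | 88-99% | 85% |

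For a 5-point one-sided change, aligned regional power is only 32% and fixed-side power about 11%.

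These figures do not model cluster extent or the small volume correction.

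**The case against.** The strongest reply is that the loss needs an effect the documents never propose. Baseline asymmetry cancels in a before-after comparison; only asymmetry of the change matters. NAC is given systemically, and neither objective 2.1.2 nor the expected 5-10% improvement names a side. This stands, and it makes the point conditional. It does not remove it, because systemic delivery does not guarantee equal response in two striata at different stages of loss. The cancellation also covers only the before-after contrast. Section 3.8.2 uses DVRs as predictors of outcome and section 3.8.3 correlates images with UPDRS. If those analyses use uptake levels, side does not cancel.

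A reader might infer that the plan commits to fixed left-right space. It does not: section 3.8.3 summarizes a typical SPM analysis and is silent on mirroring, and region laterality is unspecified. A reader might also infer that the plan treats PD as asymmetric by definition. It does not: a subject can qualify on the two features that do not mention asymmetry.

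SPM is also an addition to the primary ROI uptake values (section 3.7.1), so the largest figures above apply to a supporting analysis. A bilateral-mean ROI, which the text permits, loses less, and does at least as well as one side when the change is equal on both.

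**Conclusion.** The omission is real, and correcting it is a cheap improvement. The plan states neither an alignment step for SPM nor the laterality of its DVR regions. The cost depends on how unequal the change is: severe if purely one-sided (voxel power 93% to 12%, or 21-24% for either side; fixed-side regional power 85% to 27%), moderate at 10 and 5 (57%, or 71-83% for either side), and nil if equal. The stronger reading, that a DAT effect would in general be largely lost, is not supported. Even in the one-sided case with an even split the mean is halved, not abolished. All sizes rest on the assumed SD of change of 10, the side split and the side difference, none of which the documents give in that form.

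**What to change.** - **Side.** Identify the more affected hemisphere from baseline data only, as the one contralateral to the worse side on the baseline UPDRS, which section 3.7 already collects (assuming side-specific item scores are kept). If signs are symmetric, use the side with lower baseline striatal uptake. Keep this second rule to symmetric cases, since choosing the lower of two noisy values builds some regression to the mean into a before-after change.
- **SPM (section 3.8.3).** Normalize to a left-right symmetric template. Before testing, mirror scans where needed so that the more affected hemisphere lies on a common side, with the same flip at both visits.
- **DVR models (section 3.8.2).** Define the regions as more affected and less affected caudate and putamen.

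**Cost.** A symmetric template, one extra preprocessing step and a few sentences of text; no new subjects, visits or scans. True left-right anatomical effects can no longer be separated. If the change is equal on both sides, alignment costs no power at a given voxel or region.

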### 3.7.3 MR Spectroscopy Procedure

A brain proton magnetic resonance spectroscopic imaging ( $^1\text{H}$  MRS) will be performed in the Department of Radiology at Thomas Jefferson University and Hospital over approximately one hour. The sections of the brain scanned will be oriented obliquely along the AC/PC line. Cortical and subcortical structures such as the basal ganglia will be evaluated for the following metabolites: glutathione; N-acetylaspartate (or NAA, an indicator of neuronal integrity), creatine+phosphocreatine (CR, important in cell energetics), choline (CHO, involved in cell membrane biosynthesis/degradation), and lactate (LAC, end product of glycolysis or anaerobic metabolism). Statistical Parametric Mapping will be used to determine the differences in the concentrations of the various metabolites before and after receiving intravenous/oral NAC. In addition, connectivity and resting cerebral blood flow can be measured during the same imaging session.

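### The only test tied by name to the MRS data is a voxel-wise SPM analysis borrowed from the DaTscan plan; no regional metabolite estimate is specified, and on a small grid the borrowed rule could cost substantial power

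*Combined protocol and SAP*

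**What the plan says.** Objective 2.1.3 asks whether NAC changes oxidative stress and metabolism as measured by MRS. Section 3.7.3 frames the outcome by structure: "Cortical and subcortical structures such as the basal ganglia will be evaluated for the following metabolites", and lists five (glutathione, NAA, creatine, choline, lactate). It then assigns the comparison to SPM: "Statistical Parametric Mapping will be used to determine the differences in the concentrations of the various metabolites before and after receiving intravenous/oral NAC".

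Section 3.8.3 gives the SPM rule in text about DaTscan: "Statistically significant differences between and baseline and post-treatment scans will be assessed at each voxel with a threshold of" P<0.001, after which "clusters of voxels which survive this threshold will be assessed further using the theory of random Gaussian fields". A further sentence concerns the striatum: "Due to the limited volume of the striatum, the small volume correction will be used within SPM, allowing a more sensitive test". The section motivates this correction by the very large number of pixels in a typical brain image. It closes with the MRS sentence: "Similar analysis will be performed for the MRS data, which will compare the concentration of the specific molecules measured by MRS". The contrast given there is pre- versus post-supplementation, over three months.

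Region-level modelling is described elsewhere for other outcomes. The random coefficients model in 3.8.2 "will be fit for the DVRs in each region for the DaTSCAN binding and each neurobehavioral score". The means and SDs planned in 3.8.1 are for DVRs and clinical scores. Section 3.8.4 says that the study's analyses will be a repeated measures two-way ANOVA and linear regression, without naming outcomes, and that the study is mainly a pilot to determine effect sizes for later trials.

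**The concern.** DVRs and clinical scores get a regional or score-level model and planned summaries. The metabolites get a voxel-wise significance map, by a recipe whose rationale is specific to images with very many pixels. Section 3.8.3 argues for SPM because large regions dilute focal change and region placement is subjective. It does not argue that this suits spectroscopy. Section 1.3 reports a rise in brain glutathione after an infusion without saying that it was focal.

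Two things are at stake. A real regional change in glutathione could go undeclared because no single voxel meets a strict threshold. And the pilot could end without a regional glutathione difference and SD from which to size a later trial.

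**Working it through.** **1. The plan's own sample size.** Section 3.8.4 gives an SD of about 10%, a 5-10% improvement, 80% power, p=0.05 and 28 v 14. With 2:1 allocation, the control-arm size is (1 + 1/2) × (1.960 + 0.842)² × SD² / Δ².
- Δ = 10%: 11.8, so 12 and 24.
- Δ = 9.2%: 13.9, so 14 and 28.
- Δ = 5%: 47.1, so 48 and 96.

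The stated 28 and 14 reproduce near the top of the range. Allowing for one-third attrition, 42 / (2/3) = 63, against 65 planned. All of this concerns DVR. The documents give no MRS effect for 90 days, no MRS SD and no MRS sample size.

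**2. When is P<0.001 stricter than Bonferroni?** When 0.05/m > 0.001, that is, when m < 50 voxels. (If 0.001 is one-sided and is set against a two-sided Bonferroni, m < 25.) The grid is not stated. Assume cubic voxels of 8-15 mm and a structure of 10-30 mL, so that m = volume / edge³:
- smallest: 10 / 3.375 = 3;
- largest: 30 / 0.512 = 59;
- at 10 mm: 10 to 30.

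Under these assumptions only the finest-grid, largest-structure corner exceeds 50. For independent voxels the null chance of any P<0.001 is 1 − 0.999^m: 1.6% at m = 16, 4.9% at 50 and 9.5% at 100.

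**3. Illustrative power, 28 v 14.** The noncentrality is d × √(28 × 14 / 42) = 3.055d, with 40 df. A region-mean test at two-sided 0.05 has 80% power at d = 0.940. The same d in a single voxel has 27% power at two-sided 0.001. The table simulates a uniform effect, with a fraction of 0.3 to 0.9 of the variance shared between voxels and the effect scaled so that the region mean keeps 80% power.

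| Voxels | Any voxel at two-sided P<0.001 | 80% minus this |
|---|---|---|
| 6 | 25-39% | 41 to 55 points |
| 12 | 34-46% | 34 to 46 |
| 20 | 40-53% | 27 to 40 |
| 40 | 49-61% | 19 to 31 |
| 100 | 53-71% | 9 to 27 |
| 200 | 58-79% | 1 to 22 |
| 400 | 60-87% | −7 to 20 |

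Repeat runs agree to within a point or two. If 0.001 is one-sided, 6 to 40 voxels give 35-70%. The random-field cluster step is not modelled; it can only remove findings.

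**4. Sensitivity to effect size and contrast.** The plan words the MRS comparison as before versus after. Borrow the DVR figures (SD 10%), take one voxel, 28 pairs and two-sided tests:
- 5% effect: 72% at 0.05 v 18% at 0.001, a loss of 54 points;
- 10% effect: 99.9% v 93%, a loss of 7 points.

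**5. Sensitivity to multiplicity.** Correct the region-mean test at d = 0.940:
- five metabolites, alpha 0.05/5 = 0.01: power 57%;
- five metabolites in two structures, alpha 0.05/10 = 0.005: power 47%.

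Against the 25-61% for 6 to 40 voxels, the gap at 0.005 runs from 47 − 61 = −14 to 47 − 25 = +22 points. Left uncorrected, ten independent tests would have a familywise error of 1 − 0.95¹⁰ = 40%.

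**6. What the pilot would report.** The purpose in 3.8.4 is an effect size for later trials. The planned numerical summaries in 3.8.1 and the models in 3.8.2 do not list metabolites. The SPM output described in 3.8.3 is a map of significant differences. Values read off surviving voxels would be selected for being large, and so are no substitute for a regional mean difference and SD. This step needs no assumption about the grid.

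**The case against.** The other side has several good points.
- *SPM is not the only analysis.* Section 3.8.4 names ANOVA and regression for the whole study. This stands in part: one cannot say that no other MRS test exists. But the sentence names no outcome and sits in a paragraph built on DVR, so it leaves the two sections unreconciled.
- *Similar is not identical.* This stands. No threshold, sidedness, search volume or cluster alpha is given for MRS, and the small volume correction might carry over too. If P<0.001 does not apply, MRS has no stated threshold.
- *The coarse grid is assumed.* This stands. A search over a large grid narrows or reverses the loss, as step 3 shows.
- *The comparison is unequal.* An uncorrected 0.05 region test is a generous comparator, and deciding on every metabolite in every structure would be a flaw of its own. The plan also states no correction across metabolites for SPM, so correcting only one side is not like for like either. A multiplicity rule is nevertheless needed.
- *The regional figures could be computed anyway.* True, and 3.8.1 promises plots of all measured variables. But plots are not a prespecified estimate, and none is named.

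A reader might infer that the plan fixes P<0.001 on a coarse grid as the sole MRS test and so forfeits 20 to 55 points of power. The documents do not support that: the grid, effect, SD and voxel correlation are all absent, and reasonable choices run from no loss to more than 50 points.

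**Conclusion.** The concern holds as a gap in the analysis plan for objective 2.1.3, with a conditional power cost. From the documents alone: SPM is the only method tied to MRS by name, its rule was written for DaTscan images, no regional metabolite estimate or model is named, and 3.8.3 and 3.8.4 are not reconciled. It follows, without further assumptions, that the specified MRS output does not supply the regional effect size and SD that the pilot is meant to deliver.

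The power cost depends on assumptions. If P<0.001 is carried over, a structure holds 6 to 40 voxels and the effect is uniform and of a size that the region mean detects with 80% power, any-voxel detection is about 25-61% before the cluster step. No single figure should be quoted as the trial's loss. In a pilot, on an objective outside the primary analysis in 3.8.2, this should be corrected, and it is easy to correct.

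**What to change.** In 3.7.3 and 3.8.3:
- Make the main MRS analysis the mean concentration in each pre-named structure, comparing day-90 values between the randomised arms adjusted for baseline. Report estimates, SDs and 95% intervals.
- Name one lead metabolite and region (for example glutathione in the basal ganglia), or state a multiplicity correction across metabolites and structures.
- Keep SPM metabolite maps as supporting. State their voxel grid, threshold, sidedness, search volume and cluster alpha rather than relying on similarity to the DaTscan rule.
- Reconcile with 3.8.4 by saying which outcomes the ANOVA and regression cover.

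The cost is SAP wording and a small extra analysis. No new scans are needed, because concentrations by structure are already to be obtained. The downside is that a focal change within a structure would be seen only in the supporting maps.

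### The stated 80% power with 28 NAC and 14 control subjects does not hold across a 5-10% effect: with an SD of 10% the between-arm t-test reaches 80% only at 9.4 points and has 32% at 5 points

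*Combined protocol and SAP*

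**What the plan says.** Section 3.8.4 (Power Analysis) starts from the sponsor's earlier DAT imaging work, in which "PD patients can have variability in their DVR measures of dopamine binding of approximately 10" per cent. It continues: "If we expect a 5-10% improvement in the treatment groups, for an 80% power to detect a significant change", at p=0.05, "we would need approximately 28 subjects in the treatment arms and approximately 14 subjects in the control arm". These are completers. The section allows for one-third attrition, and 42/(1 − 1/3) = 63 fits the recruitment ceiling of 65.

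On the analysis it says "The statistical analyses for the proposed study will consist of 1) repeated measures two-way ANOVA, and 2) linear regression", and adds: "Both methods are more powerful than simple t-tests on which these estimates are based". The section opens with the caveat "We view this study primarily as a pilot study to assess changes in physiological and clinical measures". Section 3.8.5 fixes the design as a randomised comparison: "Randomization will occur via a 2:1 ratio of the NAC group and the waitlist control groups". DaTSCAN outcomes are measured at baseline and once more at about 90 days (sections 3.3.1 and 3.4.1).

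**The concern.** For a fixed SD the required sample size varies with the inverse square of the effect. Halving the effect from 10 to 5 points therefore needs about four times the subjects, and one sample size cannot give 80% power at both ends of a twofold range. The plan does not say which end it used, nor does it define the other inputs: the meaning of the 10%, the sidedness, and whether the test compares arms or time points.

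The stake is how the result is read. A reader who accepts the 80% would take a non-significant result as evidence against a 5% effect. Section 3.8.4 also says the study is meant to supply the effect size for larger trials, so an undefined SD would be carried into those designs.

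**Working it through.** **Inputs from section 3.8.4.** n1 = 28, n2 = 14, alpha 0.05, variability 10%, effects 5 to 10%. I take the effect and the variability to be on the same scale (points = % of DVR). Sidedness is not stated, so both versions are shown. Pre-post correlations r are assumptions; the documents give none.

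**Reading A: the 10% is the SD of the compared quantity, for example the SD of DVR change.** This is the direct attempt to reproduce the plan's figure.

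SE = 10 × √(1/28 + 1/14) = 3.273 points; df = 40. Power = P(T > t_crit), where T is noncentral t with noncentrality effect/SE; t_crit = 2.021 two-sided, 1.684 one-sided.

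| Effect (points) | Noncentrality | Two-sided power | One-sided power |
|---|---|---|---|
| 5 | 1.53 | 32% | 44% |
| 7.5 | 2.29 | 61% | 73% |
| 10 | 3.06 | 85% | 91% |

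Power is 80% at 9.4 points two-sided and at 8.3 points one-sided. The completers needed at 2:1 for two-sided 80% are 26+13 at 10 points, 44+22 at 7.5 and 96+48 at 5. The stated 28+14 therefore fits the top of the range only. The expected 95% CI half-width is 2.021 × 3.273 = 6.6 points.

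**Reading B: the 10% is the between-subject SD of a single scan.** The SD of change is 10√(2(1 − r)). The SD after adjusting for baseline is 10√(1 − r²), with df = 39. Two-sided results for 28 against 14:

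| r (assumed) | Power at 5 points, change score | Power at 5 points, baseline-adjusted | Difference detectable at 80%, change score | Difference detectable at 80%, baseline-adjusted |
|---|---|---|---|---|
| 0.5 | 32% | 41% | 9.4 | 8.1 |
| 0.7 | 49% | 55% | 7.3 | 6.7 |
| 0.8 | 65% | 70% | 5.9 | 5.6 |
| 0.85 | 78% | 81% | 5.1 | 5.0 |
| 0.9 | 92% | 93% | – | – |

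Reaching 80% at 5 points needs r of about 0.86 (change score) or 0.85 (baseline-adjusted). A simulation with 100,000 runs per r agreed within about 1 percentage point.

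**Reading C: a paired t-test within the 28 treated subjects, with SD of change 10%.** Noncentrality at 5 points is 0.5 × √28 = 2.65, with df = 27. Power is 82% one-sided (27 subjects suffice for 80%) and 72% two-sided (34 would be needed; 80% is reached at 5.5 points).

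**Do the planned methods close the gap?** With two time points, the group-by-time F test of a two-way repeated-measures ANOVA is the square of the change-score t. On one simulated 28/14 data set both equalled 0.3198. Under reading A its power at 5 points is therefore the same 32%. Regression adjusted for baseline does better. With SD of change 10 its residual SD is 10√((1 + r)/2), which gives 56%, 41% and 35% at 5 points for r = 0, 0.5 and 0.8. All are well below 80%.

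**The case against.** The strongest reply is that the plan meant a before-after comparison. It speaks of improvement in the treatment groups and of detecting a change, and section 3.8.3 says "differences in DaTSCAN binding between baseline and post-treatment scans will be assessed". On reading C, one-sided, 28 treated subjects cover the whole 5-10% range, and the 27 needed at 5 points nearly reproduces the stated 28. This may well be where the number came from. It still needs an unstated one-sided test, and it gives no role to the 14 randomised controls, so it cannot support the sample size of a 2:1 randomised comparison.

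A second reply is that variability in DVR measures most naturally means a single-scan SD. That is a fair reading of the words. It leaves the 80% unverifiable rather than wrong, because everything then turns on a correlation the plan does not state.

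Third, no sum in the plan is shown and the text says approximately; even on reading A, 10 points has 85% power. That is true, but the sentence gives a range, and the size fits only its top.

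Fourth, the claim that the planned methods are more powerful than t-tests is not simply false. Compared with a follow-up-only t-test, change scores gain when r exceeds 0.5, and baseline adjustment can gain as well. Whether they gain enough depends again on the missing correlation.

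Finally, the pilot label lowers the stakes. I accept that, but it does not make an explicit 80% statement correct.

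**Conclusion.** The statement is wrong as written and should be fixed. On the plain reading, a two-sided between-arm t-test with SD 10%, the 28 and 14 completers give 80% power only from 9.4 points, and 32% at 5 points. A true 5-point difference would then be missed in about 68% of such trials. One-sided testing does not rescue the lower end. The 80% at 5 points survives only with a high pre-post correlation that is not stated, or with a one-sided within-arm test that leaves out the controls.

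This does not show that the trial is certainly underpowered. If the 10% is a single-scan SD, the claim can be neither confirmed nor refuted from the documents. The figures assume that effect and variability share one scale and that 28 and 14 are evaluable subjects. Given the pilot purpose the consequence is modest, and it concerns interpretation and the assumptions passed to later trials.

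**What to change.** In section 3.8.4, define the 10% (SD of change or single-scan SD), state the sidedness, and name the between-arm difference as the comparison. Then replace the power sentence with the version that applies.

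If the 10% is the SD of change:

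> With an SD of DVR change of 10%, 28 NAC and 14 waitlist completers give 80% power (two-sided 0.05) for a between-arm difference of 9.4 points, 85% at 10 points and 32% at 5 points. The expected 95% CI half-width is about 6.6 points.

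If it is a single-scan SD:

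> With a between-subject SD of 10% for a single scan, the group-by-time test has 80% power (two-sided 0.05) for a between-arm difference of 9.4, 7.3, 5.9 or 5.1 points at a pre-post correlation of 0.5, 0.7, 0.8 or 0.85. We assume [value and source].

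Use 8.1, 6.7, 5.6 or 5.0 points instead only if the arm comparison is specified as a regression adjusted for baseline. If the estimate came from a within-arm paired test, say so, and say that it does not power the comparison of arms. Remove the sentence that the planned methods are more powerful than t-tests unless the correlation is given. Add that a non-significant result need not exclude a 5% effect.

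The cost is protocol wording, with no change in enrolment. The stated sensitivity becomes less favourable, and the sponsor has to take the SD of change or the correlation from its own earlier DAT data.
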